Stereotactic Radiosurgery, as defined by the American Society for Therapeutic Radiology and Oncology (ASTRO), the American Association of Neurological Surgeons (AANS), and the Congress of Neurological Surgeons (CNS), includes single dose SRS and well as HR delivered in 2-5 fractions over multiple days¹⁴⁻¹⁵. The majority of data supporting the use of SRS for the treatment of brain metastases has evaluated only single dose SRS and it is unclear whether the same results can be attributed to HR in 2-5 fractions. Brain metastasis amenable to single fraction SRS are typically defined as those measuring less than 3cm and producing less than 1cm of midline shift³. For brain metastasis not amenable to SRS, but for which focal brain radiation is indicated for boost or as salvage after WBRT or for avoidance of neurocognitive decline, HR provides an alternative treatment option. Current data describing the use and results of HR for the treatment of brain metastasis is limited to few retrospective series. Pater and colleagues from University of Cincinnati have demonstrated HR delivered to a dose of 30 Gy in 5 fractions to be effective and tolerable in a series of 34 patients, with a 6% (n=2) incidence of asymptomatic radiation necrosis and a 6 month actuarial local control rate of 68%¹⁶. A second series of 43 patients with metastatic breast cancer treated at Staten Island University Hospital utilized HR to a dose of 24 Gy delivered in 4 fractions, with a median survival from treatment of 7.5 months¹⁷. Recently, Wang et al. have reported on the use of HR in the setting of resected brain metastasis with resection cavities > 3cm and have demonstrated a local control rate of 80% at 6 months with the use of 24 Gy in 3 daily fraction¹⁸. With only a few series reported, the optimal dose and fractionation schedule is unknown.

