3.2 Enrollment/Randomization

This study will include 8 patient cohorts with 3 patients per cohort. The patients will be enrolled and treated following a Bayesian method permitting precise determination of the therapeutic working-dose while directly controlling the likelihood of an overdose. The method, known as Escalation with Overdose Control (EWOC), has been used to design phase I clinical trials at several cancer centers including the Fox Chase Cancer Center (PA), the Sylvester Comprehensive Cancer Center (FL), and the Winship Cancer Institute (GA) and pharmaceutical companies. EWOC was the first dose-finding procedure to directly incorporate the ethical constraint of minimizing the chance of treating patients at unacceptably high doses. Its defining property is that the expected proportion of patients treated at doses above the MTD is equal to a specified value α , the feasibility bound. This value is selected by the clinician and reflects his/her level of concern about overdosing.

The dose levels for the trial are summarized in Table 1. The dose for the first cohort of 3 patients in the trial will be the dose level 0, previous results indicating this to be a safe dose. The patient accrual will be suspended until the 4 month toxicity evaluation is completed for all previously enrolled patients. The dose for each subsequent cohort of 3 patients will be determined so that, on the basis of all available data and the target highest acceptable toxicity level of 25% DLT, the probability that it exceeds the MTD is equal to a pre-specified value α . In this trial, we set $\alpha = 0.25$ and increase α in small increments until $\alpha = 0.5$, this value being a compromise between the therapeutic aspect of the agent and its toxic side effects. The dose selected for every patient in the trial will be between the minimum dose of 27.5 Gy and the maximum allowable dose of 40 Gy. The trial will be terminated if 3 DLTs are observed in any cohort of 3 patients treated with the lowest dose level. The trial will stop after 24 patients have been enrolled and MTD will be estimated from one of the 6 specified dose levels listed in the Table 1. If no MTD is found because even the highest dose level is still considered under toxic, then the highest dose group will be considered the MTD and expanded to 12 patients.

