3.8.1 Neurologic Toxicity Assessment

1. Neurologic/CNS Toxicity will be graded according to the Common Toxicity Criteria for Adverse Events (CTCAE) version 4.03 (**Appendix B**).
2. Toxicity assessment will be made during treatment at weekly MD visits and at each follow up (1 month and 4 months after completion of radiation therapy, and every 3 months thereafter). A plus or minus 3 week window will be allowed for follow-up assessments.
3. Toxicity will be classified as immediate (within 24 hours of treatment), acute (within 4 months), or chronic (more than 4 months) based on timing after SRS.
4. Toxicities of any grade should be recorded by the radiation oncology staff on the study specific case report form at the prespecified assessment time points. All \geq grade 3 nervous system toxicity will be reported to the study principle investigator (PI).
5. Toxicities attributed to chemotherapy recorded by medical oncology staff will not be captured as study related AEs.
6. Attribution will initially be scored by the study investigators on the case report form and/or the physician seeing the patient in follow-up visit on a five point scale: 5=definitely caused by radiation treatment, 4= probably caused by radiation treatment, 3=possibly caused by radiation treatment, 2= probably not caused by radiation treatment, 1= not due to radiation treatment. Attribution will be reviewed by the PI and co-investigators. Any \geq grade 3 CNS toxicity with attribution ≥ 3 will be considered at DLT and will be reported to the DSMC. If a grade 3 CNS toxicity occurs after the patients is considered off study this will not be considered a DLT.
7. Any grade 5 toxicity will halt the study for review by the DSMC and IRB.
8. Maximal Tolerated Dose (MTD)
The MTD will be defined as the highest dose level where a grade 3 or greater with an attribution score of ≥ 3 develops in ≤ 2 of 6 patients in a dose group within 4 months of the treatment.
9. Laboratory values are not required for this protocol and will not be collected.

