4.6 Criteria for patient to be considered off study

- 4.6.1 Patient death.
- 4.6.2 Patient undergoes whole brain radiation therapy. However, we will continue to follow the patient after whole brain radiation therapy to document whether there are any enhanced toxicities with the combination of the study treatment and whole brain radiotherapy.
- 4.6.3 Patient request to come off study.

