5.2 Sample size

Dose escalation on this study will be using EWOC design. There will be 3 patients per dose escalation and enrollment will be done sequentially. A **fixed sample size of 24 will be used.**

If a patient is not able to complete follow up to the toxicity assessment point of 4 months due to a toxicity judged not to be at least possibly related to therapy, then that patient will be replaced at the same dose level by the next patient enrolled into that cohort.

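### Patients who die of disease, have WBRT or withdraw before 4 months are not replaced and have no stated DLT handling; counted as DLT-free, they bias DLT rates low and the MTD high

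*Combined protocol and SAP*

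**What the plan says.** **Size and target.** Section 3.2: "This study will include 8 patient cohorts with 3 patients per cohort". Section 5.2: "fixed sample size of 24 will be used". Escalation aims at a "target highest acceptable toxicity level of 25% DLT", and accrual pauses until every enrolled patient has had the 4-month evaluation. Section 3.8.1 item 8 defines the MTD by DLTs in no more than 2 of 6 patients within 4 months. Section 5.3.1 reports a 4-month toxicity rate with a 95% confidence interval but gives no denominator.

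**Replacement.** Sections 3.2 and 5.2 carry one rule, for a patient who cannot reach the 4-month point "due to a toxicity judged not to be at least possibly related to therapy, then that patient will be replaced".

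**Leaving the study.** Section 4.6 lists death, WBRT ("Patient undergoes whole brain radiation therapy") and patient request. None of these brings a replacement. Section 4.6.2 keeps WBRT patients in follow-up for toxicity.

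**What counts as a DLT.** Section 2.1.2 includes both acute and late CNS events of grade 3 or more with attribution 3 or more. Section 3.8.1 item 6 then states: "If a grade 3 CNS toxicity occurs after the patients is considered off study this will not be considered a DLT". Item 5 adds: "Toxicities attributed to chemotherapy recorded by medical oncology staff will not be captured as study related AEs".

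The plan has no definition of evaluable-for-DLT, no censoring rule and no partial weight.

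**The concern.** The population makes early loss likely. Eligibility admits RPA class II (4.1.4), which can include extracranial metastases and an uncontrolled primary (Appendix D). Section 3.4.6 supplies a constraint table for WBRT given after study treatment. Yet the single replacement rule addresses none of the three main routes out of the study.

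With denominators expressed as enrolled patients (3 per cohort, 6 per dose group, 24 in total), the plainest execution keeps an early loss as a patient without a DLT. Time that nobody observed is then read as safe time in each EWOC update, in the 2-of-6 rule and in the final rate. For WBRT and withdrawal, item 6 also removes grade 3 CNS events that are observed later, although section 4.6.2 goes on collecting them after WBRT. The MTD is the primary endpoint, and each escalation is a safety decision resting on three patients, so the handling needs to be fixed beforehand.

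**Working it through.** **From the plan:** 8 cohorts of 3; 24 patients; 25% target; 4-month window; 2-of-6 rule; a cited series (section 1.0) "with a median survival from treatment of 7.5 months".

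**Assumed, because the plan gives no early-loss rate:** exponential survival; DLT times uniform over months 0–4 or over months 2–4; loss independent of DLT.

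1. *The plan's own figure.* 8 × 3 = 24, as stated, with no allowance for early loss. The plan gives no prior, α step size or operating characteristics, so no error rate of its own can be reproduced.

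2. *Early deaths.* 1 − 0.5^(4/7.5) = 0.309, or 24 × 0.309 = 7.4 patients. A 12-month median gives 0.206 (5.0 patients) and a 6-month median 0.370 (8.9). The chance of at least one early death in a cohort of 3 is 1 − 0.691³ = 0.67.

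3. *Early losses counted as DLT-free.* The monthly hazard is d = ln 2/7.5 = 0.0924. The mean probability of still being on study when a DLT would occur is:
   - uniform DLTs: (1 − e^(−4d))/(4d) = 0.836
   - DLTs in months 2–4: (e^(−2d) − e^(−4d))/(2d) = 0.759

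   A true 25% reads as 0.25 × 0.836 = 20.9%, or 0.25 × 0.759 = 19.0%. A constant DLT hazard gives 21.1%; if a further 20% leave by WBRT or withdrawal (d = 0.0924 + 0.0558 = 0.148), it gives 19.1%. Conversely, the true rate that reads as 25% is 0.25/0.836 = 29.9%, or 0.25/0.759 = 32.9%.

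4. *Early losses dropped, observed DLTs kept.* DLT-free completers are 0.75 × 0.691 = 0.518. The rate becomes 0.209/(0.209 + 0.518) = 28.7% (uniform), or 0.190/(0.190 + 0.518) = 26.8% (late). The bias is now upward.

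5. *The 2-of-6 rule at a true DLT rate of 40%.* Observed rates are 0.40 × 0.836 = 0.334 and 0.40 × 0.759 = 0.304. The binomial probability of at most 2 in 6 is 54.4% with full follow-up, 67.8% with early loss, and 73.8% with early loss and late DLTs.

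6. *EWOC simulation.* 1,000 trials per case, Monte Carlo standard error at most about 1.6 points. Assumed: two-parameter logistic model; uniform priors on DLT probability at 27.5 Gy (0–0.25) and on the MTD (27.5–40 Gy); α from 0.25 to 0.50 in steps of 0.05; recommended dose = highest level not above the posterior median. True MTD 32.5 Gy, 30.9% early loss. Probability of recommending a dose above the true MTD:

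| Handling of early losses | DLTs uniform | DLTs in months 2–4 |
|---|---|---|
| Complete follow-up (no loss) | 24.4% | 24.4% |
| Counted as full non-DLT | 38.3% | 48.4% |
| Weighted by follow-up | 24.8% | 32.2% |
| Dropped | 15.1% | 18.2% |
| Replaced | 13.9% | 20.1% |

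The mean recommended dose moves from 32.4 Gy to 33.1 Gy (uniform) or 33.4 Gy (late) when losses count as non-DLTs. With a true MTD of 35 Gy the same error raises the probability from 3.7% to 8.1% or 11.6%, so the absolute effect depends strongly on where the MTD lies.

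**The case against.** **Direction.** A reader might infer that the error always favours escalation. The documents do not support that. Section 3.2 speaks of all patients completing the 4-month assessment, which a patient who has died cannot do, and section 5.3.1 names no denominator. The plan is silent, and under dropping or replacement the bias reverses (steps 4 and 6). This objection stands, and the claim is conditional.

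**The off-study bar.** It might be taken to hide toxicity in every early loss. It cannot apply to patients who have died, and death is the only loss sized here from a cited figure. For WBRT, setting aside toxicity after a second brain irradiation could be deliberate. The conflict with sections 2.1.2 and 4.6.2 remains, and naming only grade 3 leaves grades 4–5 unclear.

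**Item 5.** A reader might infer that a chemotherapy label lets an event escape attribution scoring. Items 4 and 6 largely answer this: grade 3 or higher nervous system toxicity is reported to the principal investigator, and attribution is reviewed. Section 7.2.1 adds monthly review and section 7.2.4 reporting to the DSMC. Only a clarifying clause is needed.

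**Size.** The 7.5-month median is from a breast cancer series treated with 24 Gy in 4 fractions, whereas this trial uses 5 fractions and requires KPS of at least 70. The 20% further loss, the EWOC priors and the toxicity curves are assumed. The numbers are illustrative.

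**Remedy.** Linear weighting does not fully restore the error rate when DLTs come late (32.2% against 24.4%), and it assumes that leaving is unrelated to toxicity risk. Both limits stand.

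**Conclusion.** The concern holds in conditional form. It is established from the text that replacement does not reach death from disease, WBRT or withdrawal, that no partial weight or evaluability rule exists, and that item 6 conflicts with sections 2.1.2 and 4.6.2 on later toxicity.

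That early losses count as DLT-free is the plainest reading of the fixed denominators, but it is not written. On that reading, with 31% early loss (21–37% across the assumed medians), a true 25% DLT rate reads as about 21%, or about 19% if DLTs come late or a further 20% leave. With a true MTD of 32.5 Gy, the probability of recommending too high a dose rises by about 14 points (24.4% to 38.3%). The 24.4% itself arises with complete follow-up and is not part of this problem.

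Under uniform DLT timing, the unstated choice of handling alone moves that probability between 13.9% and 38.3%. That is reason enough to settle it before the data are seen.

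**What to change.** - **Sections 3.2, 3.8.1 and 5.2:** define evaluable-for-DLT. State that a patient without a DLT who leaves before 4 months enters the EWOC likelihood with weight = observed follow-up / 4 months (time-to-event EWOC), not as a full non-DLT.
- **Section 5.3.1:** compute the 4-month rate on a matching basis that accounts for incomplete follow-up.
- **Sensitivity analyses:** (a) count grade 3 or higher CNS events after WBRT within 4 months; (b) use late-loaded weights, since linear weights correct only part of the bias when DLTs fall in months 2–4.
- **Sections 2.1.2, 3.8.1 item 6 and 4.6.2:** reconcile them on off-study toxicity, including grades 4–5. Whether such events are DLTs is a clinical choice for the sponsor.
- **Section 3.8.1 item 5:** add that every grade 3 or higher CNS event still goes through the item 6 attribution review.

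**Cost:** wording and one weight in the EWOC code, with no extra patients. Extending replacement is an alternative, but it needs more patients and shifts the bias the other way. With weighting, the effective sample size is about 24 × 0.836 = 20 with deaths alone, or 24 × 0.754 = 18 with a further 20% loss (the step 3 formula at d = 0.148), so the MTD interval is slightly wider. The weighting also assumes that early loss is non-informative, which the plan should state.

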5.3 Statistical Analysis

5.3.1 Primary Analysis: The rate of toxicities at 4 months will be calculated with 95% confidence interval (CI).

5.3.2 Secondary Analysis:

5.3.2.1 The median time to local/distant brain progression will be calculated by Kaplan-Meier method with 95% CI. For a given time point, say 4 month, the rate of local/distant progression will be calculated with 95%CI.

5.3.2.2 The median of OS time with 95% CI will be calculated by Kaplan-Meier method.

5.3.2.3 Neurocognitive effect and QOL outcomes will be regressed over time using GEE model. The population change over time (slope) will be estimated with 95%CI.

5.3.3 Patient Stratification: All enrolled patients will proceed through dose escalation as a single cohort, however patients will be analyzed as separate strata, should enrollment allow it, based on the following criteria.

5.3.3.1 Intact brain metastasis versus resection cavity.

5.3.3.2 No previous cranial irradiation versus previous WBRT or other cranial irradiation.

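### The protocol gives conflicting criteria for the MTD: a 25% DLT target under EWOC in Section 3.2, a 2-of-6 count rule in Section 3.8.1, no estimator in Section 5.3.1, and no order of precedence

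*Combined protocol and SAP*

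**What the plan says.** Sections 2.1 and 5.1.1 list the MTD as the first primary endpoint and toxicity as the second. Five pieces of current text bear on how the MTD is found.

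- **Section 3.2, dosing rule.** EWOC runs against a "target highest acceptable toxicity level of 25% DLT". Each new cohort of three receives the dose for which "the probability that it exceeds the MTD is equal to a pre-specified value" α. Here α starts at 0.25 and rises to 0.5; the size of the steps is not given.
- **Section 3.2, end of trial.** "The trial will stop after 24 patients have been enrolled and MTD will be estimated from one of the 6 specified dose levels" in Table 1. No dose-toxicity model, prior, posterior quantile or rounding rule is given. If even the top level is judged under-toxic, "then the highest dose group will be considered the MTD and expanded to 12 patients".
- **Section 3.2, enrolment example.** After a grade 3 or 4 toxicity, three more patients enter the same level. This is a step of the 3+3 type.
- **Section 3.8.1, item 8.** The MTD is defined as the highest level at which grade 3 or worse toxicity with attribution of 3 or more occurs in at most "2 of 6 patients in a dose group within 4 months of the treatment".
- **Section 5.3.1, primary analysis.** "The rate of toxicities at 4 months will be calculated with 95% confidence interval (CI"). It names no dose level and no MTD estimator.

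**The concern.** A model-based design and a count rule are different ways of answering the same question, and here they use different limits. EWOC works to a 25% DLT probability and draws on data from all doses. Item 8 looks at one level and tolerates an observed 33.3%. The enrolment example and the top-level default add two further routes to a conclusion. The section that should say how the first primary endpoint is analysed does not mention it.

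The MTD is what this trial delivers, and Section 1.0 says the results may form the basis of future trials. If the rule is not fixed in advance, the choice between sections, or of a prior or quantile, can be made after the DLTs are known. A level whose observed rate is above the stated target could then be carried forward with the protocol's own text in support.

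**Working it through.** **Inputs.** Target DLT rate 0.25 and α from 0.25 to 0.50 (Section 3.2); count rule of at most 2 in 6 (Section 3.8.1, item 8); 8 cohorts of 3 (Section 3.2); fixed total of 24 (Section 5.2); six dose levels (Table 1).

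**Step 1: the plan's own figure.** 8 × 3 = 24, which agrees with Section 5.2. The EWOC estimate of the MTD cannot be reproduced, because no model, prior or α step is given.

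**Step 2: the two limits side by side.** 2/6 = 33.3%, which is 33.3 − 25 = 8.3 points above the target. With six patients, only 0/6 and 1/6 (16.7%) are observed rates at or below 25%. The exact 95% interval for 2/6 is 4.3% to 77.7%.

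**Step 3: how often one level passes item 8.** With X ~ Binomial(6, p), P(X ≤ 2) = Σ C(6,k) p^k (1−p)^(6−k) for k = 0, 1, 2. At p = 0.25 this is 0.178 + 0.356 + 0.297 = 0.831.

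| True DLT rate | P(at most 2 of 6) |
|---|---|
| 25% | 0.83 |
| 33.3% | 0.68 |
| 40% | 0.54 |
| 50% | 0.34 |

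These are the chances that an isolated level meets the criterion. They are not the chances that it ends up as the declared MTD.

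**Step 4: what 2/6 says about the 25% target (assumed priors).** For one level with a Beta(a, b) prior, the posterior after 2/6 is Beta(a+2, b+4). The probability that the true rate exceeds 25% is:

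- uniform prior, Beta(3, 5): 0.756
- Jeffreys prior, Beta(2.5, 4.5): 0.702
- Beta(0.5, 1.5) prior with mean 25%, Beta(2.5, 5.5): 0.614

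After 1/6 the same probabilities are 0.445, 0.348 and 0.275.

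**Step 5: one data set, several answers (hypothetical data, assumed model).** Take DLTs of 0/3, 0/3, 3/12 and 2/6 at levels 0, 1, 2 and 3, so 3 + 3 + 12 + 6 = 24 patients.

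- Item 8 names level 3 (37.5 Gy). It is the highest level tried, the only one with six patients, and it has 2 of 6.
- For EWOC, assume a logistic model with a uniform prior from 0 to 0.25 on the DLT probability at 27.5 Gy and a uniform prior on the MTD from 27.5 to 40 Gy. The posterior median is 36.0 Gy, which rounds down to level 2 (35 Gy). The probability that level 3 exceeds the MTD is 0.71.
- Extend the MTD prior to 50 Gy. The median becomes 38.9 Gy, which rounds down to level 3, and that probability falls to 0.41. The 25% quantile is 35.6 Gy, which rounds down to level 2.
- Section 5.3.1, if read as one rate over all patients, reports 5/24 = 21% and identifies no level.

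The answer turns on the section, prior and quantile used, and the documents settle none of these.

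**The case against.** The case on the other side has five parts.

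1. **Section 5.3.1 may serve the second primary endpoint, toxicity, with MTD estimation left to Section 3.2.** This is a fair reading. A reader might infer that the primary analysis pools toxicity over all doses, but the text does not say so; it does not say whether the rate is per level or overall. What stands is that neither section gives an MTD estimator.

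2. **The count rule need not clash with EWOC on numbers of patients.** EWOC can repeat a level, and the enrolment example takes a level to six. The rule could also be read as a proportion, or as applying to six or more. A reader might infer that the rule can usually not be applied, but how often a level has six patients depends on priors, α steps and rounding that the protocol does not give. What stands is that item 8 has no stated rule for 3, 9 or 12 patients.

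3. **The bound α governs dose assignment, not the final choice of MTD.** This is correct. One might compare 0.61 to 0.76 with 0.25 to 0.50 and conclude that EWOC forbids a level with 2/6. The documents do not support that: α is not applied to selection, the priors are assumed, and EWOC uses data from all doses. The comparison shows only that a conflict is possible.

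4. **Two DLTs in six are compatible with the target.** At a true 25%, P(X ≥ 2) = 1 − 0.534 = 0.47. Observing 2/6 is therefore not evidence by itself that a level is too toxic.

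5. **Any small-sample rule will sometimes select a level above target.** True, and this is not the complaint. The complaint is an acceptance limit above the stated target, beside a second rule, with nothing to say which applies.

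**Conclusion.** The conflict is in the current text and needs no modelling to establish. Section 3.2 sets a 25% target and promises an estimate without a method. Section 3.8.1, item 8, defines the MTD by a count that accepts 33.3%. The enrolment example and the top-level default follow further rules, Section 5.3.1 has no MTD estimator, and no order of precedence is given. The same data can therefore yield different MTDs, and a level with an observed DLT rate 8.3 points above the target can be declared the MTD.

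The passing probabilities in Step 3 are exact for a single level with six independent patients; a level with a true 40% rate passes slightly more often than not. The figures of 0.61 to 0.76 and the example in Step 5 depend on assumed priors and, in Step 5, on an assumed model and invented data. They illustrate the conflict and do not measure how often it would occur. Whether 25% or 33% is the right limit is not judged here.

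**What to change.** Reconcile Section 3.2 (including the enrolment example and the top-level default), Section 3.8.1, item 8, and Section 5.3.1 to one MTD definition with one target DLT rate. The sponsor decides which applies.

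If EWOC is kept:

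- State the dose-toxicity model, the priors, the posterior quantile that serves as the MTD estimate, and the rule that maps it to a Table 1 level.
- Replace item 8, the expansion step in the example and the top-level default, or align them with that estimator.

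If a count rule is to prevail instead, say so in Section 3.2, restate the target to match, and cover every number of patients that a level can have.

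In Section 5.3.1, name the primary MTD analysis. Under EWOC this is the stated estimator with a 95% credible interval. Report 4-month DLT counts for each dose level with exact (Clopper-Pearson) confidence intervals, so that the toxicity rate is not taken for a single rate across doses.

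The cost is wording and a little analysis work. No extra patients or data are needed.
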